**Intensive Models of HCV Care for Injection Drug Users
PREVAIL Study**

Version Number: 1.0

01 September 2012

NCT Number: NCT01857245

Injection drug users (IDUs) constitute 60% of the approximately 5 million people in the U.S. infected with hepatitis C virus (HCV). HCV is the leading cause of liver failure and transplantation in the U.S., and mortality and health care costs due to HCV are expected to increase over the next two decades. Successful HCV treatment leading to sustained viral response (SVR) is associated with decreased progression of liver disease and increased survival, but to date successful treatment of IDUs has been limited.

Although past HCV therapies have been relatively ineffective in genotype-1 infected patients (the most common genotype in the U.S.), newer regimens are substantially improved. With the addition of direct-acting antiviral agents, HCV treatment delivered within large clinical trials leads to SVR or cure in over 90% of genotype-1 infected patients, compared to 45% with previous regimens. However, SVR rates are as low as 14% in real-world settings (pegylated interferon and ribavirin). Initial triple therapy HCV regimens were associated with increased dosing frequency (three times daily), pill burden (up to 20 pills daily), and side effects. Newer regimens such as fixed-dose ledipasvir and sofosbuvir are dosed once daily and have minimal side effects. Nevertheless, IDUs may still have lower adherence and high rates of treatment discontinuation, and many of those who fail to attain an SVR will develop drug resistance.

If HCV treatment continues to be delivered within current models of care, most IDUs will not only fail treatment and develop resistance, but may transmit drug resistant viruses to others, leading to new reservoirs of drug resistant virus. Though a growing number of studies now provide support for using interferon-based HCV treatment regimens in IDUs, none have determined the best model for delivering treatment, and this lack of data has contributed to physician reluctance to offer HCV treatment to IDUs. To reduce HCV prevalence, decrease HCV transmission leading to new infections, decrease mortality and health-care costs, and eliminate disparities in HCV-related care, effective HCV treatment must be provided to IDUs.

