The above data demonstrate: (1) our ability to enroll and retain HCV-infected IDUs; (2) efficacy of enhanced mDOT v. standard mDOT; and (3) promising early outcomes with telaprevir-based therapy. However, because this pilot RCT was not powered to demonstrate increased SVR with mDOT (and both arms included some degree of DOT), we now propose a definitive study to determine if DOT is associated with increased SVR for genotype-1 patients, and whether DOT is cost-effective.¹²⁹ We will have sufficient power to answer this question as treatment for genotype-1 patients is more effective (SVR=75%),⁴⁶ we will include only genotype-1 patients, and all medications will be self-administered in the proposed TAU arm.

D.1.5. Concurrent Group Treatment (CGT). In 2009, we implemented a group treatment model of HCV care. To date, 39 patients have initiated CGT (including 34 enrolled in the mDOT study described above). Early treatment outcomes are promising, with 89% of patients completing at least 80% of planned treatment duration, and only 2 patients discontinuing treatment because of side effects. Of the first 20 patients who initiated CGT, 80% achieved an end of treatment response and 55% achieved SVR, including 57% of those

with genotype-1 (half active drug users).¹³⁰ Eight CGT patients have initiated telaprevir-based regimens, 7 of 8 had 4 week HCV VL <43 IU, 5 out of 8 had undetectable VL, with one discontinuing treatment. These data demonstrate that CGT is a promising model of care for treating IDUs. However, since patients were not randomized, it is possible that CGT patients were more motivated than others. The 2 x 2 figure demonstrates the effects of each intervention (mDOT and CGT), as well as of their interaction. When

subjects were treated individually with mDOT, or when the subjects were treated with CGT (without mDOT), adherence and virological outcomes were better than without either intervention. However, the additive effects of mDOT and CGT appear modest. For this reason, as well as to increase generalizability, in the proposed study we will evaluate 2 models of intensive care: mDOT (both IFN and oral medications) and CGT (IFN directly-administered and oral meds self-administered). Both models must be rigorously tested to determine whether intensive models of care are superior to standard on-site care for achieving SVR.

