D.3. Setting: Einstein and Montefiore Division of Substance Abuse (DoSA). DoSA is a clinical, research, and teaching division of Einstein's Department of Psychiatry and Behavioral Sciences. DoSA operates a comprehensive substance abuse treatment program providing pharmacotherapy and related services to about 4200 adults (≥ 18 years) with current narcotic addiction (typically heroin). The primary focus is treatment of opiate dependence with methadone, and the average methadone pick-up schedule is 5 times per week. At present, DoSA operates 12 clinics in 5 Bronx communities. The treatment paradigm relies on integrating general and HCV- and HIV-related medical, substance abuse, and mental health services under one roof. Multiple RCTs have been conducted in DoSA. Both recruitment and research visits will occur at DoSA. With [name] (HCV Medical Director), [name] (DoSA Research Director), and [name] (DoSA Medical Director), participant recruitment and private office space for research visits will be ensured.

D.4. Participants. Most DoSA patients are Hispanic (59%) or black (24%), male (62%), and live under the federal poverty line (81%). Mean age is 47 years. Approximately 65% (n=2730) are HCV-infected, and 75% of those have chronic HCV (n=2048); 70% have genotype-1 (n=1434), and 80% of those are HIV-negative (n=1147). We anticipate 800 new admissions over the 3-year recruitment period, representing another 216 HCV-monoinfected genotype-1 patients.

Table 1. Inclusion and Exclusion Criteria (also see Human Subjects)

Inclusion Criteria	Exclusion Criteria

 HIV-negative Willing to receive HCV treatment on-site Initiating treatment with fixed dose (sofosbuvir and ledipasvir) Receiving methadone in clinic at least once per week Age 18 or older Able to provide informed consent English or Spanish speaking 	
 Pregnant or breast-feeding

D.5. Recruitment. Recruitment (as with other successful studies conducted in this setting)^{129,132,142} will be both active and passive; for active recruitment DoSA medical providers will inform genotype-1 HCV-infected subjects about the study and assist with referral, and for passive recruitment subjects will self-refer. Self-referred subjects will meet with their provider to determine whether starting HCV treatment is appropriate.

Determination of eligibility.

Initial screening visit and informed consent:

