
 Obtain oral consent for brief screening using Einstein Committee on Clinical Investigations (IRB) screening consent template Brief screen in private room in methadone clinic to determine eligibility Discuss study procedures, risks and benefits of study participation Obtain written consent for 1) clinical trial participation; 2) study staff to use protected health information from methadone clinic records; 3) study staff to disclose protected health information in event of psychiatric distress
Methadone clinic chart review:

 Laboratory test results: HCV Ab, HCV viral load, HIV (within 1 year), HCV genotype/subtype, IL28B, APRI and FibroSURE (biomarker tests for liver fibrosis) Methadone clinic attendance and dose
Second screening visit (medical eligibility determination by [name]):

 Review of HCV-related labs (as above) and fibroscan or liver biopsy (if available) Review of HCV Treatment Evaluation Flow Sheet to confirm no previous HCV treatment and planned on-site treatment regimen: fixed dose (sofosbuvir and ledipasvir) Participants who meet all eligibility criteria scheduled for a baseline visit Randomization (stratified, blocked) generated by centralized computer program

D.6. Participant tracking and retention. We have extensive experience following HCV- and HIV-infected drug users in studies. In our ongoing RCT of directly observed HCV treatment, 24 week follow-up was 92%.¹²⁹ In our completed RCT of directly observed HAART, 24-week follow-up was 86%.¹⁴² At enrollment and subsequent visits, we will record: 1) participants' address, phone number, and social security number; 2) contact information of family or friends; 3) contact information of participants' community-based organizations; 4) contact information of case managers; and 5) locations where participants "hang out".

D.7. Randomization. We will recruit 150 patients (100 on fixed-dose sofosbuvir and ledipasvir), with patients randomized to mDOT, CGT, or TAU in a 1:1:1 ratio (50 subjects in each group) in variable block sizes of 3-6 via central, computer-generated randomization. Two special randomization strategies (stratification and blocking) will be used to avert imbalances in prognostic factors, and to ensure comparison

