D.9.6. Future developments in HCV treatment. Study participants will receive state-of-the-art treatment (IFN in combination with telaprevir and ribavirin). As additional regimens become available with either more convenient dosing, fewer side effects, or increased efficacy, participants in all 3 arms will receive treatment according to best available practices. On October 10, 2014, the FDA approved fixed-dose (ledipasvir and sofosbuvir). Because rates of SVR are >95% in patients initiating treatment with fixed-dose (ledipasvir and sofosbuvir), all newly enrolled subjects will initiate treatment with this regimen. It is likely that our intensive models of care will be generalizable to IFN-sparing regimens which include only oral therapies. We recognize that HCV treatment has been greatly simplified, but issues with adherence, resistance, side effects, and cost will remain.

D.10. Data sources and collection.

D.10.1. Overview. Sources of data will include: blood and urine tests, participant interviews, medical charts, staff activity and expense logs, direct observation of staff, and electronic adherence monitors (Table 3).

D.10.2. Research visits. Research visits will occur at baseline, then every 4 weeks during the first 12 weeks of treatment, then at week 24 (if necessary), a “Final Treatment Week visit” will be conducted after the last day of treatment, and then post-treatment visits after 4, 12, and 24 weeks, for a total of up to 9 research visits. Participants will receive \$25 for each visit and an additional \$20 for visits with blood draws.

Baseline visit (Table 3). At baseline we will assess: sociodemographic and HCV clinical factors, potential mediating variables based on the IMB model, potential moderators (including psychiatric status, substance use, and unstable housing), and additional psychosocial factors hypothesized to predict adherence. The baseline visit will take approximately 3 hours. Blood will be collected at the first visit and stored for possible HCV viral load and resistance testing, and for future studies.

Follow-up visits (Table 3). Follow up visits will occur at weeks 4, 8, 12, and 24 (if necessary).

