D.11. Analytic plan. First, the success of randomization will be checked by comparing the mDOT, CGT and TAU groups on key variables, such as age, gender, ethnicity, race, HCV viral load, HCV subtype (1a vs. 1b), BMI, psychiatric history, active drug use, and social support.⁴⁶ By design, IL28B and stage of liver disease will be represented equally in each arm. Continuous variables will be compared between arms using the ANOVA or Kruskal-Wallis test, and categorical variables will be compared using chi-square or Fisher's exact tests. Variables that are not equally distributed will be included in multivariate models. In primary analysis, we will use the intention-to-treat principle, which preserves the advantages of a randomized design.

D.12.1. Hypotheses for Aim 1. We hypothesize that in the intensive intervention arms, compared to the control arm, rates of adherence, treatment completion, and SVR will be significantly higher, and that rates of resistance will be lower. We further hypothesize that the proportion of subjects in the intensive models of care arms who achieve an SVR will be equivalent to that observed in large registration trials.

D.12.2. Analytic plan for Aim 1. Adherence to DAAs, ribavirin, and IFN will be determined using electronic monitors and self report, as described above. Initially, adherence will be calculated as a single outcome for each subject, evaluated at the end of the study. We will use Chi-square tests or Fisher's exact test to compare the proportion of subjects who achieve high adherence rate ($\geq 80\%$) complete treatment, achieve SVR, and develop resistance in the three arms (mDOT, CGT, and TAU). If the omnibus equality test of adherence across the 3 groups is rejected, we will conduct the following 2 specific post-hoc pairwise tests with a Bonferroni adjusted 2-sided alpha= 0.025: mDOT vs. control, and CGT vs. control. This strategy will be applied to multivariable logistic regressions if any potential confounding variables not equally distributed between the study arms at baseline are identified.

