Adherence. Based on our pilot data, if we conservatively assume that 80% of subjects in both mDOT and CGT arms will achieve $\geq 80\%$ adherence (v. 50% in the TAU arm), we will have $> 87\%$ power to find a statistically significant difference. With the application of mixed-effects logistic regression to the repeatedly measured binary adherence outcome, power will be greater than 87% no matter how large the within-subject outcome correlation or intraclass correlation (ICC).

In our previous DOT study, mean adherence in the mDOT group was 87% (SD=12%, n=21), and mean adherence in the TAU group was 77% (SD=20%, n=19) which translates into a standardized effect size or Cohen's $d = 0.6$. Based on this effect size, the power of the mixed effects linear model for the repeatedly measured continuous adherence outcome will be greater than 90%, even if anticipated ICC is as high as 0.5.

Treatment completion. Based on our pilot data, if we assume treatment completion rates of 85% in CGT, 60% in mDOT, and 50% in TAU, we will have $> 80\%$ power to detect this difference.

SVR. We anticipate that SVR rates in the mDOT and CGT arms will be 70%, and $\leq 40\%$ in the TAU arm.^{13,70,82} The statistical power will be $> 80\%$. These are conservative estimates of effect sizes, as actual effect sizes will likely be larger because regimens now contain telaprevir which is taken 3x daily. Effects size for fixed-dose (ledipasvir and sofosbuvir) is likely to be lower.

Resistance. We estimate that 16% of intervention arm subjects v. 30% of TAU subjects will develop resistance. We are underpowered to detect this difference, and consider this an exploratory analysis.

Effectiveness of intensive models of care. We will determine the proportion (and 95% CI) of subjects in each of the intensive intervention arms to achieve SVR, and compare to results from large registration trials.

D.14. Limitations. In addition to the considerations noted in Section D., our results may not be generalizable to HCV-infected drug users not enrolled in methadone clinics. However, we believe that the intensive models we are testing, if efficacious, can and should be adopted in diverse settings and populations.

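### The >80% power for SVR in D.13 is shown only for 70% v 40%, not for the current trial, in which 100 of 150 participants take ledipasvir/sofosbuvir

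*Combined protocol and SAP*

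**What the plan says.** D.13 (SVR) gives one scenario: SVR of 70% in mDOT and in CGT, at most 40% in TAU, power above 80%. The calculation is for the three-group omnibus test, with 50 randomized and 40 completing per arm after 20% attrition. D.13 adds: "These are conservative estimates of effect sizes, as actual effect sizes will likely be larger because regimens now contain telaprevir". The sentence that closes the paragraph reads: "Effects size for fixed-dose (ledipasvir and sofosbuvir) is likely to be lower". No rate, power or detectable difference follows from it.

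D.1.4 presents the trial as the definitive test of whether DOT raises SVR: "We will have sufficient power to answer this question as treatment for genotype-1 patients is more effective (SVR=75"%). The 75% is the telaprevir-regimen result described in B.3.

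The regimen is described differently elsewhere:

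- D.7: "We will recruit 150 patients (100 on fixed-dose sofosbuvir and ledipasvir"). D.2 gives the same 100.
- Table 1, inclusion criteria: "Initiating treatment with fixed dose (sofosbuvir and ledipasvir").
- D.9.6: "Because rates of SVR are >95% in patients initiating treatment with fixed-dose (ledipasvir and sofosbuvir), all newly enrolled subjects" are to start on it. B.3 also puts its SVR above 95%.

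The opening summary warns that, even with the newer regimens, "IDUs may still have lower adherence and high rates of treatment discontinuation".

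**The concern.** The only SVR power shown rests on rates from earlier treatment. The references D.13 cites for them are described in B.1, B.4, D.1.2 and D.9.2 as interferon-era work. The reason for calling the rates conservative, thrice-daily telaprevir, does not apply to the two-thirds of participants on a once-daily regimen. For those participants D.13 says the effect will be smaller, which contradicts the claim that the assumed effect is conservative.

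D.12.2 compares SVR across arms without separating regimens, so the pooled rate in each arm determines power. If ledipasvir/sofosbuvir cures most TAU participants, little room is left for an intensive model to add, and a non-significant SVR comparison would say little about mDOT or CGT. A reader who trusts the stated power could take it as evidence of no benefit. D.13 openly labels the resistance comparison underpowered and exploratory; SVR carries no such caution.

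**Working it through.** **Inputs.** SVR of 70/70/40%, 40 completers or 50 randomized per arm, and the omnibus test come from D.13. The 100 of 150 on ledipasvir/sofosbuvir come from D.7, and SVR above 95% on that regimen from B.3 and D.9.6. The omnibus alpha is not stated; 0.05 is assumed. Both arm sizes are shown because D.13 powers on completers, whereas D.11 says "In primary analysis, we will use the intention-to-treat principle".

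**Step 1: reproduce the stated power.** For a three-group Pearson chi-square (2 df, critical value 5.99), the noncentrality is λ = n·Σ(pᵢ − p̄)² / [p̄(1 − p̄)].

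- p̄ = (0.70 + 0.70 + 0.40)/3 = 0.60, and Σ(pᵢ − p̄)² = 0.01 + 0.01 + 0.04 = 0.06.
- n = 40: λ = 40 × 0.06/0.24 = 10.0, power 81.5%.
- n = 50: λ = 50 × 0.06/0.24 = 12.5, power 89.6%.

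The stated figure holds for its inputs.

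**Step 2: can 70% and 40% be pooled rates for this mix?**

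- Intensive arm, 95% in two-thirds: a pooled 70% requires 3 × (0.70 − 0.95 × 2/3) = 0.20, so only 20% SVR in the remaining third.
- TAU: a pooled 40% requires ledipasvir/sofosbuvir SVR of at most 0.40/(2/3) = 0.60, even if nobody on an earlier regimen is cured.

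Neither fits the protocol's own figures for the regimens.

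**Step 3: power for the mix.** Assume the earlier-regimen third follows 70/70/40 and the rest take ledipasvir/sofosbuvir with 95% SVR in both intensive arms. Each arm total is the sum of two binomials, 13 + 27 at 40 per arm and 17 + 33 at 50 per arm. Power is obtained by enumerating all outcomes of the three arm totals and applying the same chi-square test.

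| TAU SVR on ledipasvir/sofosbuvir | Power, 40 per arm | Power, 50 per arm |
|---|---|---|
| 95% | 16% | 22% |
| 90% | 29% | 39% |
| 85% | 45% | 57% |
| 80% | 61% | 73% |
| 75% | 75% | 84% |
| 70% | 85% | 92% |

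Power reaches 80% at these points:

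- 40 per arm: TAU SVR of 72.5% on the new regimen. Pooled rates are (13 × 0.70 + 27 × 0.95)/40 = 86.9% and (13 × 0.40 + 27 × 0.725)/40 = 61.9%, a difference of 25 points.
- 50 per arm: TAU SVR of 77.1%. Pooled rates are 86.5% and 64.5%, a difference of 22 points.

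**Step 4: sensitivity**, as power at 40 (50) per arm.

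- Intensive arms 100%, TAU 95% on the new regimen: 33% (45%).
- Earlier third at 75/75/40, intensive arms 95% on the new regimen: 24% (34%) with TAU at 95%; 71% (82%) with TAU at 80%.
- Intensive arms 90% on the new regimen: 42% (52%) with TAU at 80%; 70% (80%) at 70%; 81% (89%) at 65%.

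**The case against.** The strongest reply is that low power is not proven. The documents give no TAU SVR on ledipasvir/sofosbuvir, and they warn of poorer adherence and discontinuation in this population. At TAU SVR of 70–75% the table gives 75–85% at 40 per arm and 84–92% at 50. The 95%/95% row has no effect in two-thirds of the sample by construction, so low power there is no planning failure. All this is correct, and it is why the point is limited to power not having been shown.

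D.13 also discloses that the effect is likely to be smaller. That gives the direction but not the size, and it sits beside an unrevised power figure and the word conservative.

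The thresholds of 72.5% and 77% depend on 95% SVR in the intensive arms. With 90%, the TAU rate needed falls to between 65% and 70% at 40 per arm and to about 70% at 50. The fixed split of regimens within arms is also a simplification, since regimen is not a stratification factor. A random split gives about 20% instead of 16% in the first row and 32% instead of 29% in the second. Neither point changes the conclusion.

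Finally, SVR is one of four Aim 1 outcomes, and adherence has its own power statement. But D.1.4 claims sufficient power for SVR specifically, and D.9.3 calls virological outcome the most important clinical outcome.

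**Conclusion.** The concern holds. Power above 80% is correct for 70/70/40, but the documents do not support it for the trial now described, and calling those inputs conservative contradicts D.13's own closing sentence. Over TAU SVR of 70–95% on ledipasvir/sofosbuvir, power runs from 85% down to 16% at 40 per arm, and from 92% down to 22% at 50. These ranges assume an omnibus alpha of 0.05, a one-third/two-thirds mix in every arm, 70/70/40 on the earlier regimens and 95% SVR in the intensive arms on the new one. The power statement must be corrected, because D.1.4 relies on it to present a definitive SVR comparison.

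**What to change.** In D.13 (SVR):

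1. State that 70% v 40%, and the power above 80%, apply only if all participants were on the earlier regimens.
2. Delete the word conservative, or limit it to participants taking telaprevir.
3. Replace the single figure with a table of power and minimum detectable SVR difference for the actual mix (100 on ledipasvir/sofosbuvir, 50 on earlier regimens), over TAU SVR of 70–95% on the new regimen, at 40 and 50 per arm. State the omnibus alpha and the assumed intensive-arm SVR, preferably with more than one value of the latter.
4. State that SVR will be reported as mDOT v TAU and CGT v TAU differences with 95% confidence intervals, so that a non-significant result can be read for what it excludes. D.13 currently promises intervals only for the proportion in each intensive arm.

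In D.1.4, refer the claim of sufficient power to that table.

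The cost is one recalculated table and a few sentences, with no added patients or visits. With 95% SVR in the intensive arms, the stated power becomes less favourable unless TAU SVR on the new regimen is about 72.5% or lower (77% at 50 per arm).
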